Primary estimand: effect of the randomised treatments on the survival duration in all subjects that are KRAS/NRAS and BRAF WT (Double negative [DN]) regardless of whether or not intercurrent events occur	OS	HR	Treatment policy strategy	FAS
Key secondary estimand: effect of the randomised treatments on the survival duration in all subjects that are KRAS/NRAS, BRAF WT and EGFR-extracellular domain WT (Triple negative [TN]) regardless of whether or not intercurrent events occur	OS	HR	Treatment policy strategy	FAS restricted to Triple negative [TN] subjects
Effect of the randomised treatments on the survival duration in all subjects that are KRAS/NRAS and BRAF WT (Double negative [DN]) before participants receive further anti-cancer therapy	OS	HR	While on treatment strategy	FAS
Effect of the randomised treatments on the survival duration in all subjects that are KRAS/NRAS, BRAF WT and EGFR-extracellular domain WT (Triple negative [TN]) before participants receive further anti-cancer therapy	OS	HR	While on treatment strategy	FAS restricted to Triple negative [TN] subjects
Effect of the randomised treatments on progression-free survival before participants receive further anti-cancer therapy	PFS	HR	While on treatment strategy	FAS
Effect of the randomised treatments on progression-free survival regardless of whether or not intercurrent events occur	PFS	HR	Treatment policy strategy	FAS
Effect of the randomised treatments on response before participants receive further anti-cancer therapy	OR DC	Risk difference	While on treatment strategy	FAS

Table (10.1.2.4.2) 1 (Cont'd) - Studied estimands

Estimand	Variable	Population level summary	Handling intercurrent events (IEs)	Population
Effect of the randomised treatments on the response duration before participants receive further anti-cancer therapy	DoR	HR	While on treatment strategy	FAS
Effect of the randomised treatments on the time from the randomisation to initiation of the next systemic anti-cancer therapy	TTNT	HR	While on treatment strategy	FAS
Effect of the randomised treatments on the time from randomisation until first radiologically confirmed tumour response (CR or PR) before participants receive further anti-cancer therapy	TTR	HR	While on treatment strategy	FAS
Effect of the randomised treatments on the time from the date of randomisation to the date when ECOG PS score of ≥ 2 is observed for the first time before participants receive further anti-cancer therapy	TtPS2	HR	While on treatment strategy	FAS

With:

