
- OS: overall survival defined as the time from date of randomisation into the study to death from any cause.
- PFS: progression-free survival defined as the time from date of randomisation until the date of the investigator-assessed radiological disease progression or death, whichever occurs first.
- OR: overall response defined as the achievement of confirmed CR or PR according to RECIST version 1.1 criteria and using investigator's tumour assessment.
- DC: disease control defined as the achievement of best response of CR or PR or SD according to RECIST version 1.1 criteria and using investigator's tumour assessment.
- DoR: duration of response defined as the time from the first documentation of confirmed tumour response (CR or PR) according to RECIST version 1.1 criteria and using investigator's tumour assessment to the first documentation of objective tumour progression or to death due to any cause.
- TTNT: time to next treatment defined as the time from the randomisation to initiation of the next systemic anti-cancer therapy.
- TTR: time to response defined as the time from randomisation until first radiologically confirmed tumour response (CR or PR) according to RECIST version 1.1 criteria and using investigator's tumour assessment.
- TtPS2: time to ECOG performance status ≥ 2 defined as the time from the date of randomisation to the date when ECOG PS score of ≥ 2 is observed for the first time.

Estimands and the way for handling IEs will be detailed in the following paragraphs.

10.1.2.4.2.1. Primary estimand based on the OS

The primary estimand of interest is the effect of the randomised treatments on the survival duration in all subjects that are KRAS/NRAS and BRAF WT (Double negative [DN]) regardless of whether or not intercurrent events occur (treatment policy strategy). The motivation for this choice is to assess the efficacy of the futuximab/modotuximab in combination with trifluridine/tipiracil compared to trifluridine/tipiracil monotherapy under the ITT principle (intercurrent events are considered to be part of the treatments being compared).

All data collected during the trial regardless of occurrence of an IE will be used. This is aligned with the treatment policy strategy.

Primary analysis

The distribution of OS will be compared between the two treatment groups using a stratified log-rank test at one-sided 2.5% level of significance (stratification factors based on IWRS data).

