The following analyses will be done:

- The distribution of DoR per investigator's tumour assessment will be compared between the two treatment groups using a stratified log-rank test at one-sided 2.5% level of significance (stratification factors based on IWRS data).
- DoR per investigator's tumour assessment for each arm will be summarized using Kaplan Meier curves and further characterised in terms of the median along with the corresponding 2-sided 95% CI for the estimate.
- The distribution of TTNT will be compared between the two treatment groups using a stratified log-rank test at one-sided 2.5% level of significance (stratification factors based on IWRS data).
- TTNT for each arm will be summarized using Kaplan Meier curves and further characterised in terms of the median along with the corresponding 2-sided 95% CI for the estimate.
- The distribution of TTR per investigator's tumour assessment will be compared between the two treatment groups using a stratified log-rank test at one-sided 2.5% level of significance (stratification factors based on IWRS data).
- TTR per investigator's tumour assessment for each arm will be summarized using Kaplan Meier curves and further characterised in terms of the median along with the corresponding 2-sided 95% CI for the estimate.
- The distribution of TtPS2 will be compared between the two treatment groups using a stratified log-rank test at one-sided 2.5% level of significance (stratification factors based on IWRS data).
- TtPS2 for each arm will be summarized using Kaplan Meier curves and further characterised in terms of the median along with the corresponding 2-sided 95% CI for the estimate.

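### Duration of response is tested between arms and labelled a full-analysis-set effect of randomised treatment, although it exists only in confirmed responders

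*Protocol*

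**What the plan says.** Protocol Section 10.1.2.4.2 defines the endpoint: "DoR: duration of response defined as the time from the first documentation of confirmed tumour response (CR or PR"), running to progression or death. Table (10.1.2.4.2) 1 states the DoR estimand as "Effect of the randomised treatments on the response duration before participants receive further anti-cancer therapy", with hazard ratio as the summary, a while-on-treatment strategy and the FAS as population. Section 10.1.2.4.2.4 then says: "The distribution of DoR per investigator's tumour assessment will be compared between the two treatment groups". The method given is the log-rank test, stratified by the factors recorded in the IWRS, with a one-sided level of 2.5%. A Kaplan-Meier curve and median with 95% CI by arm are also planned.

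The only handling rule in that subsection excludes responses recorded after an intercurrent event. Section 10.1.1.1 makes the FAS the default for efficacy in the Randomised part. Nothing restricts DoR to responders or limits it to description.

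Time to response (TTR) has the same test and the same FAS label, but a different origin: "TTR: time to response defined as the time from randomisation until first radiologically confirmed tumour response (CR or PR").

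SAP Version 2.0 (Section 1) reports that the Randomised part was cancelled and refers to the protocol for everything about it.

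**The concern.** A participant who never responds has no DoR, so the analysed set cannot be the FAS. The set actually compared is the confirmed responders in each arm, and membership depends on an outcome that the treatment is meant to change. If the experimental regimen adds responders of poorer prognosis than those who would respond on control, its average DoR falls although nobody's duration was shortened. A log-rank test on such groups can favour control because the experimental arm produced more responses. Readers would take the result for a randomised effect, because the estimand table describes it that way.

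**Working it through.** **1. Planned figure.** None exists for DoR. The stated power concerns overall survival (383 events, 90% power). It reproduces: with the stated spending functions, efficacy bounds are Z = 2.511 and 1.993, and power is 90.0% at a hazard ratio of 8.5/12. The DoR point does not touch it.

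**2. Time origins.**

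| Endpoint | Clock starts | Who has a value | Population in table |
|---|---|---|---|
| DoR | first confirmed response | responders only | FAS (impossible) |
| TTR | randomisation | everyone, event or censored | FAS (possible) |

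**3. Size of the compared groups.** Section 10.2 gives 500 randomised 1:1, so 250 per arm. All response rates here are assumptions. The 9.6% is the 9/6 mg/kg arm of the Phase 2 study (Section 2.2.2). The 37% is panitumumab plus trifluridine/tipiracil in participants not previously given anti-EGFR therapy (Section 2.3.2). The 1% to 5% brackets the 2.9% of the Phase 2 control arm.

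- Arm A: 250 × 0.096 = 24; 250 × 0.37 = 92.5.
- Arm B: 250 × 0.01 = 2.5; 250 × 0.05 = 12.5.
- Share of the FAS: (24 + 2.5)/500 = 5.3%, up to (92.5 + 12.5)/500 = 21%.

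The three binary stratification factors make 8 strata, so Arm B would have 2.5/8 = 0.3 to 12.5/8 = 1.6 responders per stratum. A stratum with responders in only one arm contributes nothing to the test.

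**4. Selection effect.** Simulation with 250 per arm, an unstratified log-rank test among responders and about 4,000 trials per row. Each participant has a standard normal prognosis score. Response is a threshold on a second normal variable correlated r with that score. Duration is exponential multiplied by exp(s × score), under the same law in both arms, so treatment has no effect on any duration. Nominal error is 2.5% in each direction.

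| Response rate A vs B | r, s | Wrongly favours A | Wrongly favours B | Median DoR A vs B (months) |
|---|---|---|---|---|
| 9.6% vs 2.9% | 0.5, 0.7 | 3.2% | 4.3% | 7.2 vs 8.7 |
| 9.6% vs 2.9% | 0.7, 1.0 | 1.3% | 6.6% | 13.0 vs 19.1 |
| 37% vs 2.9% | 0.5, 0.7 | 1.2% | 9.8% | 5.5 vs 8.6 |
| 37% vs 5% | 0.7, 1.0 | 0.1% | 33.1% | 7.6 vs 16.1 |
| 9.6% vs 9.6% | 0.5, 0.7 | 3.0% | 3.0% | 7.1 vs 7.1 |
| 37% vs 37% | 0.7, 1.0 | 2.6% | 2.2% | 7.7 vs 7.6 |

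With equal response rates the error stays near nominal. With unequal rates and response related to prognosis it moves against the arm with more responders. With unequal rates but r = 0 the medians agree (about 3.8 months in each arm) and the shift reverses: 4.5% to 5.7% wrongly favour A and 1.4% to 2.0% wrongly favour B. That part reflects very small, unbalanced groups, not selection.

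**5. Information.** Power for a DoR hazard ratio of 0.5, if every responder has an event, is Φ(0.693 × √(a·b/(a+b)) − 1.96), where a and b are the responder counts.

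- a = 24, b = 2.5: a·b/(a+b) = 2.26, power 18%.
- a = 92.5, b = 12.5: a·b/(a+b) = 11.0, power 63%.

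This is imprecision, a separate matter from the bias in step 4.

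**6. TTR.** A FAS log-rank test with non-responders censored rejected in 2.0% of 1,000 simulated trials at 2.9% in both arms, consistent with 2.5%. At 9.6% vs 2.9% it rejected in 88%, so it largely repeats the response-rate comparison.

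**The case against.** **Any statistician will compute DoR in responders whatever the table says.** Probably so, and the Kaplan-Meier median already planned is a sound summary. That settles the calculation but not the reading: the table still calls it an effect of randomised treatment, and the test still compares selected groups.

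**Little inferential weight rests on it.** This stands. Section 10.1.2.4.2 sets the secondary objectives as estimating effects. Section 10.1.2.4.2.2 confines the closed testing sequence to overall survival in double-negative and then triple-negative participants. No Cox model is listed for DoR; the hazard ratio appears only in the table.

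**The response rates are borrowed.** This also stands. The Phase 2 rates are for evaluable patients; on all randomised they are 8/86 = 9.3% and 2/85 = 2.4%. That study gave futuximab/modotuximab alone, against capecitabine, 5-FU or best supportive care. Neither arm is an arm of this trial, which is why a range is shown.

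**Stronger readings to resist.** A reader might infer that TTR shares the defect because it has the same test and label. The documents do not support that: TTR starts at randomisation, its FAS label is correct, and a FAS log-rank test compares the randomised groups. Moving TTR to responders only would create the selection problem. A reader might also infer that a reported result is biased; SAP Version 2.0 cancels the Randomised part and keeps only best overall response for efficacy.

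**Conclusion.** The point holds for DoR on the text alone. The stated population is impossible for the endpoint as defined, and the planned test is not a randomised comparison. How far it could mislead depends on assumptions that the documents cannot settle: the two response rates and how strongly response tracks prognosis. Under the prognosis-related settings simulated, control was wrongly favoured in 4.3% to 33% of trials and the experimental arm in 0.1% to 3.2%. With equal response rates the distortion largely disappears.

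For TTR only a gap remains: the protocol does not say how non-responders, or deaths and progressions before response, enter the analysis.

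Severity is minor. DoR supports no alpha-controlled claim and no DoR comparison will be run. The protocol is nevertheless the only available specification of the Randomised part, and a design that reuses it would carry the error forward.

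**What to change.** - Section 10.1.2.4.2.4: delete the DoR log-rank test. Keep the Kaplan-Meier median with 95% CI by arm, described as descriptive among confirmed responders.
- Table (10.1.2.4.2) 1, DoR row: change the population from FAS to confirmed responders, remove the hazard ratio, and drop the wording about an effect of the randomised treatments.
- If an arm comparison is wanted, use mean time in response in the FAS, with non-responders counted as zero, over a pre-specified time horizon.
- TTR: keep the FAS label and the test. At most, add a rule for non-responders and for death or progression before response.

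The cost is wording and the loss of one secondary test. The survival sample size, boundaries and alpha are unaffected.

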10.1.2.5. Quality of Life analysis

Endpoints:

- EORTC QLQ-C30 questionnaire.
- EORTC EQ-5D-5L questionnaire.

10.1.2.5.1. Analysis

10.1.2.5.1.1. EORTC QLQ-C30

The raw QoL data will be scored according to the EORTC scoring manual and the change in score from baseline in the global health status (GHS) scale is identified as the primary QoL variable of interest.

The completion and compliance rates will be summarised by treatment group for each scheduled assessment timepoints.

The completion rate is defined as the rate of participants who completed the QoL instrument among participants in the QoL analysis set.

The compliance rate is defined as the rate of participants who completed the QoL instrument among participants still on treatment at each visit.

Baseline values and changes in scores from baseline (GHS and each sub-scale score) will be summarized at each scheduled assessment time point descriptively.

A repeated-measures mixed-effects model (SAS PROC MIXED) that includes terms for treatment arms, baseline stratification factors, baseline sub-scale score and time of visit will be used to compare the two treatment groups with respect to changes from baseline in the GHS and each sub-scale score longitudinally over time.

Time to definitive ≥ 10 points deterioration from baseline in the GHS and in each sub-scale, will be compared between the two treatment arms in the QoL analysis set using the stratified log-rank test at a 2-sided 5% level of significance (strata based on IWRS data). Death will be considered to be a deterioration event of QoL. Participants receiving any further anti-neoplastic therapy before definitive worsening will be censored at the date of their last QoL assessment before starting this therapy. Participants who have not worsened as of the cut-off date for the analysis will be censored at the date of their last assessment (questionnaire) before the cut-off. Participants without evaluable questionnaire at baseline will be censored at their randomisation date + 1 day. The distributions will be described using Kaplan-Meier curves including the median time to definitive 10 points deterioration.

10.1.2.5.1.2. EORTC EQ-5D-5L

The dimensional 5-level system will be converted into a single index utility score: the utility index will be derived according to specific country algorithms.

The completion and compliance rates will be summarised by treatment group for each scheduled assessment timepoints.

The completion rate is defined as the rate of participants with evaluable EQ-5D-5L assessment among participants of the EQ-5D-5L analysis set.

The compliance rate is defined as the rate of participants with evaluable EQ-5D-5L assessment among participants still on treatment at each visit.

A breakdown table to include the proportions of reported problems (no problems, slight problems, moderate problems, severe problems, or extreme problems) at baseline *versus* each scheduled assessment timepoint will be presented in each dimension of EQ-5D-5L by treatment arms in the EQ-5D-5L analysis set.

Baseline values and changes in score from baseline in EQ-5D-5L VAS and EQ-5D-5L health utility index will be presented by treatment arms at each scheduled assessment timepoint by descriptive statistics (N, mean/proportion median, SD, Q1, Q3).

A repeated-measures mixed-effects model (SAS PROC MIXED) that includes terms for treatment, baseline stratification factors, baseline score and time of visit will be used to compare the two treatment groups in the EQ-5D-5L analysis set with respect to changes from baseline in the EQ-5D-5L VAS and EQ-5D-5L health utility index.

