9.6. Quality of Life Assessments (Only for Randomised part)

EORTC Quality of Life Questionnaire - Core Questionnaire (EORTC QLQ-C30) ([Appendix 6](#)) and EQ-5D-5L ([Appendix 5](#)) will be completed by the participant on an e-PRO, independently of the study personnel at the following time points, at the beginning of each visit at the following time point:

- Inclusion.
- After the end of cycle 1 (C2D1)
- Every 2 cycles during the treatment period (C3D1, C5D1...).
- WV.
- Every 2 months during the follow-up period, until death or until end of the study is reached (whichever occur first).

Participants will be provided with specific instructions in order to be comfortable with the e-PRO device and enhance the quality of the data. In case the participant is not able to use e-PRO, a caregiver (not a medical/investigator staff) will be allowed to read the questions to the

participant and to collect the answer without any interpretation of the questions and the answers. Data entered by the participant will be sent to a central database via a secured transfer.

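### The QoL compliance rate has no denominator at the withdrawal and follow-up assessments, and the QoL mixed models, listing main effects only, cannot show how the arm difference changes over time

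*Protocol*

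**What the plan says.** **Model.** Protocol 10.1.2.5.1.1 (QLQ-C30) specifies "A repeated-measures mixed-effects model (SAS PROC MIXED) that includes terms for treatment arms, baseline stratification factors, baseline sub-scale score and time of visit", to compare the arms "with respect to changes from baseline in the GHS and each sub-scale score longitudinally over time". Change in global health status (GHS) is named as the primary QoL variable. Section 10.1.2.5.1.2 (EQ-5D-5L) specifies a model "that includes terms for treatment, baseline stratification factors, baseline score and time of visit". No interaction, covariance structure or coding of visit (categorical or continuous) is given for either.

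**Compliance.** For the QLQ-C30: "The compliance rate is defined as the rate of participants who completed the QoL instrument among participants still on treatment at each visit". For the EQ-5D-5L: "The compliance rate is defined as the rate of participants with evaluable EQ-5D-5L assessment among participants still on treatment at each visit". Both sections require completion and compliance by arm at each scheduled timepoint. Completion is taken over the whole analysis set of the instrument.

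**Schedule.** Section 9.6 and footnote 13 of Table (4.1.2) 2 place forms at baseline, C2D1, C3D1 and every second cycle after that, at the withdrawal visit, and then "Every 2 months during the follow-up period, until death or until end of the study is reached (whichever occur first").

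**Other QoL analyses.** The protocol also plans descriptive summaries of change at each timepoint for both instruments and, for the QLQ-C30, a stratified log-rank test of time to definitive deterioration of at least 10 points.

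**SAP.** Version 2.0 states in its Introduction that the randomised part was cancelled, and it marks QoL as not applicable (section 3.6 and Appendix D).

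**The concern.** Compliance tells a reader how far the QoL results can be trusted. Its usual form is forms received over forms expected. Here the denominator disappears once treatment stops, although collection continues to death or study end. Those later forms are the ones most likely to be missing for reasons linked to health, and the arms are expected to leave treatment at different rates.

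The model is said to compare the arms over time, but a main-effects model holds the arm difference equal at every visit. A constant difference is doubtful here. In the earlier phase 2 trial (Protocol 2.2.2), dermatologic events affected 92.9% of the 9/6 mg/kg arm and 10.3% of controls. Section 6.1.2.1.1 says infusion-reaction risk is highest at the first dose. The early futility analysis assumes a longer median PFS with the combination. Early toxicity followed by later tumour control is plausible, though the documents give no QoL trajectory.

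**Working it through.** **1. Is there a plan figure to reproduce?** No QoL sample size, SD, effect or power is stated. The medians borrowed below come from design figures that do reproduce:
- Protocol 10.1.2.8, PFS HR 0.525, one-sided 0.10, 95% power: 4 × (1.2816 + 1.6449)² / (ln 0.525)² = 34.26 / 0.415 = 82.5, so 83 events, as stated.
- Protocol 10.2, 383 OS events with the Table (10.2) 1 boundaries: simulated power is 0.896 at HR 0.71 and 0.900 at HR 8.5/12, against the stated 90%.

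**2. Compliance, rule against schedule (no assumption needed).**

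| Form due at | Anyone due the form on treatment? | Compliance |
|---|---|---|
| C2D1, C3D1, C5D1, ... | yes | defined |
| Withdrawal visit | no, it follows treatment withdrawal | denominator empty |
| Every 8 weeks in follow-up | no | denominator empty |

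**3. How many forms does this leave out?** Use S(t) = exp(−ln 2 × t / median), with t = weeks × 7 / 30.44 months, at 14 visits: week 4, then weeks 8, 16, ..., 104. Time alive uses the planned OS medians (12 and 8.5 months, Protocol 10.2). Time on treatment uses the PFS medians (4 and 2.1 months, Protocol 10.1.2.8) as a proxy, which is an assumption. Sums of S(t) over the 14 visits:
- Arm A: alive 7.627, on treatment 3.474; share off treatment 1 − 3.474/7.627 = 54%.
- Arm B: alive 6.227, on treatment 1.935; share off treatment 1 − 1.935/6.227 = 69%.
- Both: 1 − 5.409/13.854 = 61%.

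**4. Does completion fill the gap?** Its denominator keeps participants who have died. At week 24 the same OS medians give 73% (A) and 64% (B) alive. Perfect return by every living participant would thus show as roughly 73% and 64% completion, a gap between arms caused by deaths alone. (The analysis set requires one post-baseline form, so the true figures would be somewhat higher.)

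**5. Weight of each visit in the common arm difference.** With independent visits the weight is proportional to nA × nB / (nA + nB). With correlated visits, generalised least-squares weights were used (categorical visit, monotone dropout, compound symmetry, correlation 0 to 0.7). Equal weighting would put 2/14 = 14% on weeks 4 and 8.

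| Forms returned | Weight on weeks 4 and 8 |
|---|---|
| On treatment only | 61% to 74% |
| Plus 30% after treatment | 41% to 61% |
| Plus 50% after treatment | 35% to 55% |
| All, until death | 27% to 41% |

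**6. Does the sign of a pooled value follow?** Take invented true differences of −8, −4, +2, then +6 from week 24 on, with independent visits:
- On-treatment forms cut off at C7D1: weights 0.391, 0.308, 0.188, 0.113; pooled −3.3 (70% of weight on the first two visits).
- On-treatment forms to week 104: −2.1 (61%).
- Forms returned until death: +2.3 (27%).

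The sign depends on the return assumption.

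**The case against.** The strongest reply has five parts.

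- **Other analyses cover the time course.** By-visit summaries are planned for both instruments, and a deterioration test for the QLQ-C30. This stands in part. A reader might infer that the whole QoL comparison reduces to one early-weighted average. The documents do not support that: the limitation applies to the mixed models only. Even so, the descriptive tables carry no model-based arm contrast, and the log-rank test answers a different question.
- **Completion covers follow-up.** It does, so a reader should not conclude that missing follow-up forms go unmeasured. Because its denominator includes the dead, it cannot separate non-return from death.
- **Compliance may be meant as an on-treatment measure.** That is a natural reading of the definition, but the same sections promise the rate at every scheduled timepoint. One of the two has to change.
- **The term list may not be exhaustive.** Protocol 10.1 defers implementation to the SAP, and the abbreviations in SAP version 2.0 still include MMRM and TUDD, so a fuller specification may once have existed. It cannot be seen, and neither available document contains an interaction.
- **The size rests on assumptions.** This stands. PFS is a proxy, and return rates and correlation are unknown. The synopsis's approximate 6.5 months of treatment, used as the median in both arms, lowers the independent-visit weight on weeks 4 and 8 to 34% over the 14 visits. That opposite effects would cancel, or that a particular negative value would be reported, is a tempting inference that step 6 does not bear out.

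**Conclusion.** The compliance definition is wrong as written, for both instruments. The contradiction is in the text and needs no assumption. Its extent, about 61% of forms due from living participants (54% in Arm A, 69% in Arm B), assumes exponential curves, PFS as time on treatment and the planned OS medians.

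The model point is a cheap improvement. As listed, each model gives one common arm difference and cannot show change over time. That average leaned towards early visits in every scenario run, with 27% to 74% of the weight on weeks 4 and 8 against 14% under equal weighting. The documents support no particular pooled value or sign.

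QoL is a secondary endpoint outside the tested hierarchy of OS in the double-negative and then the triple-negative population. With the randomised part cancelled, no analysis under SAP version 2.0 is affected. The point matters for the protocol text and for any reuse of it.

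**What to change.** 1. **Compliance.** For both instruments, define it at each timepoint as forms completed divided by participants alive, not withdrawn and due a form then, including the withdrawal and follow-up visits. Keep completion as a second measure and state that its denominator includes deaths.
2. **Model.** Add treatment-by-visit and baseline-by-visit terms, treat scheduled visit as categorical, and report the arm difference at each scheduled visit with its confidence interval.
3. **GHS contrast.** Prespecify one visit, or an equally weighted average over named visits. Which to choose is for the sponsor to justify: an early visit is well populated but ignores later change.
4. **Covariance.** State the structure and a fallback order, since an unstructured matrix over many sparse late visits may not converge.

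The by-visit tables and the time-to-deterioration test stay as planned. The cost is protocol and SAP wording plus wider intervals at late visits, with no new data collection.
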